1.3 SCHEDULE OF ACTIVITIES (SOA)

A schedule of activities is provided in Table 1 below, with further detail provided in Section 8.

TABLE 1 : SCHEDULE OF ACTIVITIES (SOA)

Procedures	Screening	Enrollment Day 0	Discharge Day 0 till discharge	30-Day Visit Day 30 +/- 14 days	6-Month Visit Day 180 +/-30 days	1-Year Visit Day 365 +/-60 days	2-Year Visit Day 730 +/-90 days	3-Year Visit Day 1095 +/-90 days	4-Year Visit Day 1460 +/-90 days	5-Year Visit Day 1825 +/-90 days
Informed consent	X									
Demographics	X									
Medical history	X									
Device Implantation		X								
Vitals (including height and weight)	X	X		X	X	X	X	X	X	X
Serum creatinine	X			X	X	X	X	X	X	X
Serum Pregnancy Test ^a	X									
CTA ^b	X			X	X	X	X	X	X	X
X-ray ^c				X		X		X		X
Complete Case Report Forms (CRFs)/Data collection	X	X	X	X	X	X	X	X	X	X
Adverse event review and evaluation		X	X	X	X	X	X	X	X	X

a: Only for women of childbearing potential

b: For follow-up (not screening), a non-contrast CT and duplex ultrasound may be done in place of the CTA, if the subject has renal insufficiency.

c: 2-view abdominal (left and right oblique)

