³ Defined as, at the conclusion of the procedure, a > 10mm difference between the top of the Nellix stents, or the top of a visceral stent being > 14mm below the Nellix stent (the bag shelf is 4mm below the top of the Nellix stents).

⁴ Concomitant procedures, including those for infrequently encountered circumstances, may be anticipated and prepared for as part of a comprehensive endovascular approach

of adjunctive stents that are part of the defined system, does not result in technical failure.⁵

- c. Successful withdrawal (i.e., successful withdrawal of the delivery systems without the need for unanticipated corrective intervention related to withdrawal).

Multiple events occurring to a subject are considered a single subject failure for the purposes of calculating the composite one-month rate, as the rate is based on the total number of subjects. Since none of these variables are restricted by imaging requirements for detection, the cutoff date for the endpoint is exactly 30 days from the index procedure.

3.2 1-YEAR PRIMARY ENDPOINT

The primary 1-year endpoint is a blend of safety and effectiveness indicators. The endpoint is defined as the absence of:

- Abdominal aortic aneurysm rupture (0 - 365 days);
- Aneurysm-related mortality (0 – 365 days)
- Imaging-determined events at the 12-month imaging window. These do not require an intervention within 12 months to count as events:
 - Type I or Type III endoleak
 - Migration⁶ > 10mm
 - Sac Expansion⁷ > 5mm
 - Loss of Patency (100% occlusion) in Branches⁸, Nellix, or iliac limbs not seen at the index procedure
- Open conversion through day 365

⁵ Examples of acceptable procedures include:

- Placing an additional stent (Verta or Lifestent) to correct kink in visceral vessel (or a kink in the stent resulting from the vessel anatomy) or to smooth transition from Verta to visceral vessel (transition stenting)
- Placing an additional stent (Verta or Lifestent) to treat pre-existing visceral artery stenosis (spot stenting)
- Placing Verta stent within initial Verta stent due to length discrepancy, need to achieve a Verta length not covered by available lengths, or inadequate initial seal
- Placing Ovation limb to extend Nellix in order to obtain an adequate distal seal;
- Coiling of non-treated branch vessels
- Ballooning of any vessel or stent

⁶ As measured by the proximal end of the Nellix stents relative to the reference artery

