⁷ As measured across the maximum transverse sac diameter relative to the 1-month scan

⁸ Branches refer to stents in the left renal artery, right renal artery, and superior mesenteric artery

- Other major device-related⁹ surgical or endovascular re-interventions through day 365 for:
 - Type I or III endoleak, or gutters
 - Migration
 - Thrombotic events/Occlusions - complete loss of patency in any of the components of the ChEVAS System due to thrombotic events and/or device deformation
 - Device deformation resulting from fracture, that leads to clinical sequelae of vessel stenosis progressing to decreased perfusion, or puncturing of graft material leading to endoleak
 - Relining of the Nellix Stents to correct stenosis or kink
 - Mal-deployed device that leads to clinical sequelae of migration, endoleak, or thrombosis
 - Device infection

Non-major interventions are not included in the endpoint:

- Endovascular intervention for branch stenosis (within the stent or distal to the stent) for a reason other than stent fracture
- Interventions for Type II endoleaks
- Non endovascular treatments for procedural complications that are non-device specific, e.g., seroma, surgical site infection etc.

The 1-year endpoint is a collection of variables that may be detected at any time or require imaging to be detected. As such, variables are evaluated differently for the “1-year” timeframe. Variables lacking imaging restrictions (rupture, mortality, interventions) are evaluated until day 365 for the 1-year endpoint as the exact day of the event will be known. Onset dates for imaging-driven variables are unknown (they have may occurred at any time prior to the imaging scan that detected them) and thus are evaluated at the one-year imaging window as determined by the scan date. Presence of positive imaging-related findings within the 1-month or 6-month imaging windows does not factor into the endpoint analysis. Rather, the endpoint analysis restricts positive findings to only those within the 1-year imaging window. Imaging results used in the endpoint analysis will be sourced from core lab assessments.

In contrast to classic EVAR studies that analyze safety at 1 month and effectiveness at 1 year, the ChEVAS study is designed to evaluate both safety and effectiveness across dual endpoints (thus, passing both endpoints will indicate the trial has demonstrated safety and effectiveness).

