3.3.4 OUTCOMES

Additional outcomes will be collected for each follow-up time point through 5 years post procedure. All outcomes will be differentiated, where appropriate, by the stents involved (Nellix vs. Verta stents)

- Mortality (all-cause and aneurysm-related)
- MAE Individual Components
- Aneurysm Rupture
- Conversion to Open Repair
- Adverse Events
- Renal Function (assessed via creatinine and eGFR)
- All Types of Endoleak (Ia, Ib, Ic, II, III, IV, or unknown)

- Gutters
- Device Patency and Integrity
 - Stenosis
 - Occlusion
 - Kinking
 - Fracture
- Aneurysm Sac Diameter
- Migration (e.g., migration > 5 mm, migration > 10 mm, clinically significant migration)
- Secondary Procedures
 - All Types of Endoleaks
 - Device stenosis/occlusion
 - Device kink
 - Device fracture
 - Luminal thrombus
 - Rupture
 - Migration
 - Aneurysm sac expansion
 - Device defect
 - Gutters

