An external Core Lab will be used for this study. The Core Lab will be responsible for reading both screening and follow-up scans provided by the sites. Their findings and measurements will be recorded into the Electronic Data Capture (EDC) system. The results from the Core Lab will be used in the assessment for device-related findings, including endoleaks, aneurysm enlargement, gutters, kinking, and stent fractures. Occlusion will be primarily reported by the site due to a clinical finding (e.g., claudication) and confirmed via angiogram with the subject in the operating theater (i.e., utilizing CT scan results would under-report this event).

¹⁰ Secondary ChEVAS does not count as prior ChEVAS experience

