8.3 SCHEDULE OF ACTIVITIES

Implantation

The subject is enrolled into the study upon the first attempt to insert the Nellix catheter into the patient. The subject is treated with the ChEVAS System, following the IFU. Procedural data is collected, including concomitant procedures, and device accountability information.

Discharge

Upon discharge of the subject from the hospital, ward stay information is collected, along with creatinine levels, blood pressure, and medications.

Follow-up visits (30 days, 6 months, 1 year, 2 years, 3 years, 4 years, and 5 years)

The site will schedule and conduct a clinical visit with each subject within the required follow-up visit windows (**Table 4**), where vitals will be collected. Required imaging and labs must also be conducted during the required visit window. The required imaging and labs include:

- CT with contrast (CTA), 3mm slice thickness maximum
 - Note: In cases of renal insufficiency, CT without contrast (3mm slice thickness maximum) and a duplex ultrasound may be conducted instead of the CTA
- X-ray (30-day, 1 year, 3 year and 5 year): 2-view abdominal (left and right oblique)
- Serum Creatinine

In addition to imaging, at each follow-up visit, medication categories will be collected, along with Adverse Event collection and assessment

The following table (**Table 4**) shows the required visit schedule. Subjects must have their required scans, visits, and labs completed within the given time frames.

TABLE 4 : VISIT WINDOW SCHEDULE

Visit	Beginning of visit window	Target Day	End of Visit Window
1 Month	16	30	44
6 Month	150	180	210
1 Year	305	365	425
2 Years	640	730	820
3 Years	1005	1095	1185
4 Years	1370	1460	1550
5 Years	1735	1825	1915

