8.4 SAFETY AND OTHER ASSESSMENTS

Information collected at the following procedures/evaluations, as applicable:

- **Physical examination** Including weight, blood pressure, medication assessment. If patient exhibits potential neurological change, the patient will undergo an mRS exam for endpoint analysis
- **Blood Laboratory Analysis** Including Serum Creatinine, eGFR (calculated)
- **Contrast-enhanced CT scan:** imaging requirements include slice thickness of $\leq 3\text{mm}$; axial, coronary, sagittal views. To ensure consistency, below are the requirements for CT acquisition:
 - Only high resolution, contrast-enhanced spiral CT scans are acceptable. Sites are required to use radiation reduction techniques
 - Data must be uncompressed
 - **Preferred maximum slice spacing is 2mm.** In no case should it exceed 3mm
 - The preferred protocol, shown below, is easier to attain with a multi-row scanner. If the preferred protocol cannot be used, an alternate protocol is provided.
 - Instruct patient not to move during scan. Do not move table height, position, or field of view during scan. If such movement occurs, repeat scan in its entirety.

Parameter	Preferred	Alternate
Scan Mode	Helical/Spiral	
Scan Parameters	140kVp, Auto mA, 0.5sec	140kVp, 280mA (min), 1.0sec
Collimation	0.625 to 2mm	3mm
Slice Spacing	0.625 to 2mm	3mm
Superior Extent	Cervical Spine – C2 or base of ears	
Inferior Extent	Lesser trochanter of femur	
Patient Instruction	Single breath hold	1 st hold: above celiac to bifurcation 2 nd hold: bifurcation to lesser trochanter
Contrast*	Standard non-ionic	
Volume and Rate	150mL at 3 to 4 mL/sec or as per institutional standards	
Scan Delay	ROI - threshold 90Hu in aorta	
Field of View	Large body	
Window Level	400/40	

*For those subjects with renal insufficiency, a non-contrast CT and duplex ultrasound will be acceptable.

- **Procedural Information:** The Index Procedure CRF will capture all relevant procedural data including access times and types, anesthesia type, all devices implanted, any adjunctive devices used, timing of procedural events, post-procedural findings, complications and concomitant procedures performed, blood loss, contrast volume, fluoroscopy time and any observations on the procedure
- **Adverse Events:** these will be captured at any point after enrollment until study exit. This is determined by the time the patient enters the operating room or catheter lab.

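### The section 8.4 CT table requires C2 coverage at every visit, although no Core Lab-read follow-up CT endpoint or outcome lies above the visceral aorta

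*Combined protocol and SAP*

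**What the plan says.** Protocol section 8.4 presents its CT table as the acquisition requirements, for the sake of consistency. The Superior Extent row reads "Cervical Spine – C2 or base of ears" and the Inferior Extent row ends at the lesser trochanter. Neither row separates screening from follow-up. The table's footnote states: "For those subjects with renal insufficiency, a non-contrast CT and duplex ultrasound will be acceptable". Table 1 note b in section 1.3 gives the same allowance but limits when it applies: "For follow-up (not screening), a non-contrast CT and duplex ultrasound may be done in place of the CTA".

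Table 1 and section 8.3 schedule CT at screening, 30 days, 6 months and yearly from 1 to 5 years.

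Section 3.2 lists "Imaging-determined events at the 12-month imaging window": Type I or III endoleak, migration, sac expansion and loss of patency. On the stents at issue, footnote 8 says "Branches refer to stents in the left renal artery, right renal artery, and superior mesenteric artery". Section 4.1 has Core Lab results feed the "assessment for device-related findings, including endoleaks, aneurysm enlargement, gutters, kinking, and stent fractures". The thoracic aorta and great vessels appear in the eligibility criteria: inclusion 17 (section 5.1) and exclusion 12 (section 5.2).

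**The concern.** A scan from C2 to the lesser trochanter takes in the neck and chest as well as the repair. At screening this has a clear purpose, because the chimney stents are placed through the upper extremity and the route has to be assessed. At follow-up the protocol names no reading that needs it.

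What is at stake is repeated exposure of the neck and chest over five years. Section 8.4 tells sites to reduce radiation, yet the same section fixes the scan range, so a site that shortened a follow-up scan would depart from a listed requirement. A scan spoiled by movement has to be redone over its whole length, neck and chest included. Nothing statistical is at stake.

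**Working it through.** **Step 1. Does the table govern follow-up scans?** It never says that it applies at all visits, so this has to be inferred. Its footnote accepts non-contrast CT plus duplex in renal insufficiency, and Table 1 note b permits that substitution at follow-up and rules it out at screening. A screening-only table would have no use for the footnote. The documents give no other CT range.

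**Step 2. At what level does each follow-up CT reading lie?**

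| Reading | Where defined | Level |
|---|---|---|
| Endoleak, gutters | 3.2, 3.3.4, 4.1, 8.5.11 | Around the EndoBags, chimney stents and distal seal |
| Migration | 3.2 footnote 6, 8.5.11 | Nellix stents against a reference artery; 8.5.11 uses the distal renal artery |
| Sac diameter | 3.2 footnote 7, 8.5.11 | Aneurysm sac |
| Patency | 3.2 and footnote 8, 3.3.4 | Renal and SMA stents, Nellix stents, iliac limbs |
| Stenosis, kinking, fracture | 3.3.4, 4.1 | Implanted components |

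The highest planned landing zone is below the celiac (section 1.1; section 5.1 footnote 11). Section 4.1 has occlusion reported mainly by the site and confirmed by angiogram, but the vessels concerned are the same. The follow-up X-ray in section 8.3 is abdominal only.

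**Step 3. Where is thoracic anatomy used?** In inclusion 17 (access route) and exclusion 12 (descending thoracic aneurysm). Both are settled before implantation.

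**Step 4. Scan counts.**

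- The plan's sample size (section 9.2): 103 evaluable with about 14% drop-out gives 103 / (1 − 0.14) = 119.8, rounded up to 120. This matches the plan.
- Scheduled CTs per subject (Table 1): 1 screening + 7 follow-up = 8.
- All follow-up CTs: 7 × 120 = 840, made up of 3 × 120 = 360 through 1 year and 4 × 120 = 480 in years 2 to 5.
- From 6 months to 5 years only: 6 × 120 = 720, and 720 / 840 = 86%.
- Illustration of attrition, assuming that 103 subjects contribute every scan: 7 × 103 = 721, or 6 × 103 = 618 from 6 months on.

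The up to 30 infrarenal roll-in subjects are left out because they follow the Appendix 1 protocol. Repeats for movement are not counted.

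**The case against.** **Access route.** Sections 2.3.3.1.1 and 2.4.1 describe embolic and stroke risk from crossing the arch and vertebral arteries, and section 8.5.6 anticipates arterial damage and access-site complications. Section 3.3.4 collects adverse events at every visit. So a reader should not infer that every follow-up outcome lies at or below the visceral aorta; that holds only for the CT readings. This makes early upper coverage a reasonable choice and is why the 30-day scan is left to the sponsor. It does not explain C2 coverage from 6 months to 5 years.

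**Stroke.** The major adverse event definition in section 8.5.10 asks for imaging confirmation. That is triggered by a neurological deficit and is not tied to the scheduled CT. A scan that stops at C2 or the base of the ears does not image the brain.

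**Uniformity.** Consistency is a stated reason for a single specification. It supports the same technique at each site, and a range fixed by visit would be just as consistent.

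**The count.** Reading 840 as the number of unneeded neck-and-chest scans goes too far. Aborted cases need no 30-day CT and leave the study, and converted subjects also exit (section 7.1). The table sits under contrast-enhanced CT, so whether its range binds non-contrast scans is unstated. The extent row shows one entry, which reads as common to both columns; if it belonged only to Preferred, the point would hold for that column alone. This objection stands, and the counts are ceilings.

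**Unseen sources.** Section 4.1 also refers to the instructions for use and institutional standards. A reason for C2 at follow-up could lie there, but the protocol states none.

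**Breath-holds.** The Alternate column's first hold begins above the celiac, leaving the range from C2 to that level unassigned. One might infer that screening scans will miss the thoracic aorta. That requires a site to disregard the extent row, and Core Lab and Case Review Board review (sections 8.1, 8.2) would probably catch a short scan. It is a matter of wording.

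**Conclusion.** The point holds as a design refinement worth making. The protocol requires neck and chest coverage at follow-up visits where no stated CT analysis uses it. At most 6 scheduled scans per subject are affected from 6 months on, or 7 if 30 days is included: ceilings of 720 and 840 in 120 subjects before attrition. This assumes that the table applies at follow-up, as its footnote implies, and that its extent row binds both columns and the non-contrast scans.

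A reader might infer a measurable harm or dose saving. The documents give no dose by body region, and radiation reduction is already required, so neither can be derived. Nor does the point touch the hypotheses, power or analysis populations.

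**What to change.** Make the Superior Extent row visit-specific, for both columns:

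- Screening: keep C2 or base of ears.
- 30 days: the sponsor decides. Keep C2 if early coverage of upper-extremity access complications is wanted, and state that reason; otherwise use the follow-up range.
- 6 months to 5 years: start above the celiac and above the proximal end of the implant and chimney stents, with wider coverage only when clinically indicated.

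State whether the range also applies to non-contrast scans. As a minor clarification, add an upper breath-hold to the Alternate column for scans that start at C2.

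The cost is an edit to two rows of one table, with no added scan, visit or endpoint. The downside is that some incidental chest or access findings may be missed on routine scans. The trial does not analyse these by CT, and wider coverage stays available on indication. If the sponsor has a reason for C2 throughout follow-up, the protocol should state it.

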8.5 ADVERSE EVENTS AND SERIOUS ADVERSE EVENTS

Adverse events will be entered on the applicable eCRF and in the patient's corresponding binder. The date of onset, classification, coding, outcome, severity, device and procedure relationship, and action taken are requested to be identified by the PI, as well as a brief narrative to provide further details regarding the event presentation, diagnostics, course and resolution.

8.5.1 DEFINITION OF ADVERSE EVENTS (AE)

An adverse event (AE) is any undesirable clinical occurrence in a patient enrolled in the trial that does not necessarily have a causal relationship with the treatment. An AE can therefore be any unintended sign, symptom or disease temporally associated with the use of an investigational product, whether or not related to the use of the product (ISO 14155)

For purposes of this study, the following events are not considered adverse events, because they are expected to occur in conjunction with the index procedure or are associated with subjects undergoing customary, standard of care endovascular AAA repair procedures:

- Early post-operative pain (within 24 hours of index procedure) at the access site and/or related to position on procedure table
- Post-anesthesia/conscious sedation emesis, nausea, or headache (within 24 hours of index procedure)
- Electrolyte imbalance without clinical sequelae following index procedure, even if requiring brief correction
- Low grade temperature increase (<101.0°F)
- Hematocrit decrease from baseline of less than 6 points (2 grams of hemoglobin) that remains above 30% and is not associated with hemodynamic changes and does not require transfusion
- Blood loss not requiring transfusion and not resulting in decreased hematocrit
- Minor, localized tenderness, swelling, induration, bruising, erythema, hematoma etc. at vascular access site that does not require surgical intervention, evacuation, transfusion or antibiotics
- Prophylactic administration of atropine
- Prophylactic pacing
- Isolated, non-sustained PVCs/PACs
- Non-sustained arrhythmia not requiring treatment or intervention
- Hypotension or hypertension not requiring treatment or intervention
- Atelectasis not requiring treatment
- Prolonged hospitalization due to logistical delays relating to discharge to a skilled nursing facility, care facility, rehabilitation center, etc.

The Investigator and/or IRB/EC may require that these events are reported as adverse events. In this case, the Investigator should report these observations based on their medical judgment and requirements of the IRB/EC.

8.5.2 DEFINITION OF SERIOUS ADVERSE EVENTS (SAE)

A serious adverse event (SAE) is an adverse event that:

- Led to death
- Led to a serious deterioration in the health of the subject that:
 - Resulted in life threatening illness or injury
 - Resulted in a permanent impairment of a body structure or a body function
 - Required in-patient hospitalization or a prolongation of existing hospitalization
- Resulted in medical or surgical endovascular procedure to prevent permanent impairment to a body structure or a body function
- Led to fetal distress, fetal death, or a congenital abnormality or birth defect

8.5.3 SEVERITY OF EVENT

The Severity of an AE is a clinical determination of the event intensity. The severity assessment for a clinical AE should be completed using the following guidelines:

- **Mild (+1)** – Awareness of sign or symptom, but easily tolerated.
- **Moderate (+2)** – Discomfort enough to cause interference with usual activity
- **Severe (+3)** – Incapacitating with inability to work or do usual activity.

8.5.4 CLASSIFICATION OF AN ADVERSE EVENT

All AEs will have a classification determined by the PI. The following options will be available for classification:

- Bleeding/Anemia
- Bowel
- Cardiac
- Chimney Device
- Endoleak
- Malignancies
- Miscellaneous
- Nellix Device
- Neurological
- Pulmonary
- Renal
- Surgical Site Wound
- Urogenital
- Vascular

